3.1.1 Dose Limiting Toxicity

For the purposes of dose escalation a dose limiting toxicity (DLT) is defined as:

- Any Grade 3 or greater toxicity that is possibly related to the vaccine and as defined by Common Terminology Criteria for Adverse Events (CTCAE) Version 5.0 with the exception of transient (≤ 24 hours) Grade 3 flu-like symptoms or fever, which is controlled with medical management or transient (≤ 24 hours) Grade 3 fatigue, skin reactions or rash, headache, nausea, emesis that resolves to Grade ≤ 1 or asymptomatic grade 3 amylase/lipase elevation. For purposes of dose escalation the DLT evaluation period will be for 3 weeks following the first dose of drug.

Subjects experiencing a DLT will be removed from protocol therapy.

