3.1.2 Dose De-Escalation

Up to six patients will be enrolled at dose level 1. If ≤ 1 of 6 patients experience a DLT, initiation of the dose expansion phase will occur. If ≥ 2 of 3 or 6 experience DLT in the initial dose level, then dose de-escalation will occur. Up to six patients will be enrolled at the lower dose level (-1) (1×10^{11} VP). If ≤ 1 of 6 patients experience a DLT, then the maximum tolerated (MTD) will be declared at this dose, and initiation of the dose expansion phase will occur. If ≥ 2 of 3 or 6 experience DLT at dose level -1, then an amendment may be written to evaluate a further dose de-escalation.

In the second part, dose expansion will occur when the MTD has been determined. An additional 4 subjects will be enrolled in the dose expansion component of the trial, for a total of 10 subjects treated at the MTD.

A schematic overview of the study is shown in Figure 6.

In the initial component of the study, 3 to 6 subjects will be sequentially enrolled starting at the standard dose at dose level 1. During enrollment at each dose level, there will be a minimum of 3 days between enrolling successive subjects. DLTs will be monitored continuously.

Dose levels are shown in Table 4. No intra-patient dose escalations are permitted.

Table 4: Dose Levels for Each ETBX VP

Dose Level (DL)	ETBX VP
Standard (1)	5×10^{11}
-1	1×10^{11}

[figure not shown]
Standard dose (DL 1) (5×10^{11} VP):

- If ≤ 1 of the initial 6 subjects experience a DLT, dose expansion will commence.
- If >1 of the initial 3 subjects, or if ≥ 2 of the 6 total subjects experience a DLT, enrollment at DL -1 will commence.

Dose de-escalation DL -1 (1×10^{11} VP):

- If ≤ 1 of the initial 6 subjects experience a DLT, this dose level will be defined as the MTD and dose expansion will commence.
- If >1 of the initial 3 subjects, or if ≥ 2 of the 6 total subjects experience a DLT, then a protocol amendment may be written to evaluate a further dose de-escalation..

Figure 6: Study Design and Treatment Schema

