3.3 DOSE DELAY OR DISCONTINUATION

Applies to events occurring outside of the DLT evaluation period

- Patients must have recovered to \leq grade 2 for injection site reaction or grade \leq 1 for any other toxicity related to the vaccines for the parameters used to assess levels of organ function required for eligibility (see Section [2](#)) after each vaccination in order to receive a subsequent vaccination. Patients will receive a diary card to record injections site reactions (see [Appendix B](#)).
If \geq grade 3 nonautoimmune toxicity attributable to the vaccines persists for $>$ 42 days, the patient will not receive further vaccine inoculations and will be removed from the protocol treatment and followed for resolution of toxicity and immune/survival endpoints.
- Patients who develop any \geq grade 3 autoimmunity, not related to a therapeutic response, will be removed from the protocol treatment and followed for resolution of toxicity and immune/survival endpoints.
- Patients who develop any grade 4 toxicity attributable to the vaccines will be removed from the protocol treatment and followed for resolution of toxicity and immune/survival endpoints.
- Dosing of the vaccines injections should be given on schedule every 3 weeks (Week 0, 3, and 6), and then bi-monthly (every 8 weeks) boosts for up to a year. In the event of conflicts, a +/- 1 week window is acceptable.
- For unrelated acute illnesses present at the time of a scheduled vaccination, dosing can be delayed until symptoms subside, or the subject may be withdrawn at the discretion of the Investigator; delays up to 4 weeks are considered acceptable in this setting.

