3.5 STUDY CALENDAR

Assessment	Screening	Treatment (Every 3-Week Dosing)			Bimonthly_Boosters (Every 8-Week Dosing)						End of Treatment (within 90 days after the last vaccine) ^m	Follow Up ^l
		Baselin e/0	3	6	14	22	30	38	46	54		
Study Week	Day -28 to -1ⁿ											
Clinic Visit	X	X ^c	X	X	X	X	X	X	X	X	X	
Informed Consent	X ^a											
Inclusion/Exclusion	X											
Demographics	X											
Confirmation of diagnosis (path report)	X											
Physical Examination, Height ^b , Weight, ECOG	X ^c	X ^c	X	X	X	X	X	X	X	X	X	
Medical History ^d	X	X ^c										
Concomitant Medications	X	X ^c	X	X	X	X	X	X	X	X	X	
Vital Signs ^e	X	X ^c	X	X	X	X	X	X	X	X	X	
12-Lead ECG	X				X	X	X	X	X	X	X	
Confirm Contraceptive Measures ^f	X											
Study Drug Injection/ Injection Site Reaction Monitoring ^g		X	X	X	X	X	X	X	X	X	X	

Assessment	Screening	Treatment (Every 3-Week Dosing)			Bimonthly_Boosters (Every 8-Week Dosing)						End of Treatment (within 90 days after the last vaccine) ^m	Follow Up ^l
		Baseline e/0	3	6	14	22	30	38	46	54		
Study Week	Day -28 to -1ⁿ	Baseline e/0	3	6	14	22	30	38	46	54		
Dispensation of Subject Diary Card ^h		X										
Review of Subject Diary Card ^h			X									
Tumor Imaging ⁱ	X			X	X	X	X	X	X	X		
Pregnancy Test ^j	X ^{c,n}	X ^c	X	X	X	X	X	X	X	X	X	
Urinalysis	X ⁿ										X	
Chemistry Panel	X ^{c,n}	X ^c	X	X	X	X	X	X	X	X	X	
CBC, Differential, Platelets	X ^{c,n}	X ^c	X	X	X	X	X	X	X	X	X	
Coagulation	X ⁿ										X	
Serum Virology (HIV, HBV, HCV) ^k	X ⁿ											
Adverse Events		X	X	X	X	X	X	X	X	X	X	
Exploratory Immune Analysis		X		X	X		X				X	
Telephone Follow Up												X

^a Informed consent may be obtained on D0 after eligibility is confirmed and other screening protocols may be used to obtain screening labs and procedures as per NCI's internal SOP

^b Height will only be assessed at screening.

^c If the assessment is performed within 24 hours prior to the first dosing, a second assessment at baseline/week 0 can be omitted.

^d Complete medical history will be evaluated at screening and includes current and past cardiac and pulmonary history, documentation of diagnosis including history of current and prior cancers, prior treatment(s), and prior radiologic studies. Any new events in the medical history will be evaluated at baseline..

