8.4.4 Safety Analysis

DLTs will be evaluated continuously in a dose level. An overall assessment of whether to de-escalate to the next dose level will be made at least 1 week after the last subject in the previous dose level has received their first injection. A dose level will be considered safe if $< 33\%$ of subjects treated at a dose level experience a DLT (i.e., 0 of 3, ≤ 1 of 6, ≤ 2 of 9, ≤ 3 of 10). Safety will be evaluated in 3 or 6 subjects at each dose level in the dose escalation component of the study. Safety will continue to be monitored among additional subjects treated at the MTD or HTD in the dose expansion component of the study. A subject will be considered evaluable for safety if treated with at least one injection. DLTs will be observed for 1 week.

Safety endpoints will be analyzed as summary statistics during treatment and/or as change scores from baseline assessments. AEs will be coded as defined in the Medical Dictionary for Regulatory Activities (MedDRA). All AEs will be recorded and tabulated following each treatment (vaccine injection). AEs will be recorded by severity, frequency, and relationship to the study intervention and will be presented by System Organ Class (SOC) designations and preferred term groupings. Information on each AE will include start date, stop date, severity, relationship, expectedness, outcome, and duration. Adverse events leading to premature discontinuation from the study intervention and serious treatment-emergent AEs will be presented either in a Table or a Listing.

In addition, overall safety will be assessed by descriptive analyses using tabulated frequencies of AEs by grade using CTCAE Version 5.0 within dose levels and for the overall study population in terms of treatment-emergent AEs, SAEs, and clinically significant changes in safety laboratory tests, physical examinations, ECGs, and vital signs.

The safety events listed in section [8.4.6.2](#) will trigger a temporary suspension of the study injections.:

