11.1.5.3 Administration

Each of the three ETBX vaccines will be administered on Weeks 0, 3, and 6 followed by bi-monthly booster vaccines for up to a year. All study drug administration treatments should occur within ± 7 days of the planned visit date.

ETBX-011 will be administered by subcutaneous injection in the upper arm after preparation of the site with alcohol. A 1 to ½ inch, 20- to 25- gauge needle should be used for administration.

ETBX-051 will be administered by subcutaneous injection in the anterolateral upper thigh after preparation of the site with alcohol. A 1 to ½ inch, 20- to 25- gauge needle should be used for administration. It is preferred to administer ETBX-051 and ETBX-061 in separate thighs. However, if administered in the same thigh, injection sites should be separated by at least 5 cm.

ETBX-061 will be administered by subcutaneous injection in the anterolateral upper thigh after preparation of the site with alcohol. A 1 to ½ inch, 20- to 25- gauge needle should be used for administration. It is preferred to administer ETBX-051 and ETBX-061 in separate thighs. However, if administered in the same thigh, injections sites should be separated by at least 5 cm.

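### The DLT period is 3 weeks in section 3.1.1 but 1 week in section 8.4.4, so a qualifying event on days 8–21 may go uncounted when the choice between expansion and de-escalation is made

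*Combined protocol and SAP*

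**What the plan says.** Section 3.1.1 (Dose Limiting Toxicity) sets the window: "For purposes of dose escalation the DLT evaluation period will be for 3 weeks following the first dose of drug". A subject with a DLT comes off protocol therapy.

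Section 8.4.4 (Safety Analysis) sets another: "DLTs will be observed for 1 week". The same section says that the assessment of whether to de-escalate "will be made at least 1 week after the last subject in the previous dose level has received their first injection".

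Sections 3.1.2 and 8.2 give the decision rule without a window: ≤1 of 6 with a DLT opens the expansion phase, and ≥2 of 6 leads to de-escalation. On conduct, section 3.1.2 says that "there will be a minimum of 3 days between enrolling successive subjects" and that "DLTs will be monitored continuously".

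In the section 3.5 calendar, the first visit after week 0 is at week 3. The first post-dose chemistry panel and blood count (the row "CBC, Differential, Platelets") fall at that visit. Dosing visits may move by a week: section 3.3 says "In the event of conflicts, a +/- 1 week window is acceptable", and section 11.1.5.3 gives the same 7-day tolerance.

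**The concern.** The two windows differ by two weeks, both stand in current text, and no sentence says which governs. A possibly related Grade 3 or higher event on days 8–21, outside the exceptions listed in section 3.1.1, is a DLT under that section. Under section 8.4.4 it may not be counted when the dose level is judged.

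Three things depend on the answer:

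- **The primary endpoint.** DLTs and the MTD (or highest tested dose) are the first primary endpoint in section 1.1.4. With six subjects, one or two events decide the result.
- **The timing of the decision.** Even if the 3-week definition governs, section 8.4.4 permits an assessment before most subjects have finished 3 weeks.
- **Individual care.** A DLT removes the subject from therapy. Section 3.3 covers only events outside the DLT period and allows some subjects to continue after recovery from a Grade 3 event. The boundary decides which rule applies.

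Section 1.2.8 records that this combination has not been given to humans before.

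**Working it through.** **Which window fits the rest of the plan.** The calendar has no visit and no laboratory test between week 0 and week 3, so a laboratory DLT has no scheduled test inside a 1-week window. The diary card covers 7 days after the first injections, but only local reactions, pain medication, chills and temperature. The schedule therefore fits 3 weeks better than 1 week.

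**Plan figure.** The only sample-size figure is the enrolment ceiling in section 8.2: 12 dose-finding + 4 expansion + 16 screen failures = 32. It reproduces and does not depend on the window. The plan states no DLT rate, onset distribution or operating characteristics.

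**Follow-up at the earliest permitted decision.** Inputs are six subjects, first injections spaced as enrolment is spaced (an assumption), a decision 7 days after the last first injection, and follow-up capped at 21 days. Full follow-up is 6 × 21 = 126 subject-days.

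| Spacing | Decision day | Subject-days observed | Incomplete windows |
|---|---|---|---|
| 3 days (minimum, section 3.1.2) | 5×3+7 = 22 | 21+19+16+13+10+7 = 86 (68%) | 5 of 6 |
| Weekly (assumed) | 5×7+7 = 42 | 4×21+14+7 = 105 (83%) | 2 of 6 |
| Two-weekly (assumed) | 5×14+7 = 77 | 5×21+7 = 112 (89%) | 1 of 6 |

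**Chance of passing, as illustration.** Let p be the true 3-week DLT probability and F(t) the share of DLTs with onset by day t.

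- Full windows: P(X ≤ 1) = (1−p)^6 + 6p(1−p)^5. At p = 1/3 this is 0.088 + 0.263 = 0.351.
- Earliest decision: subject i contributes probability p·F(tᵢ), where tᵢ is that subject's follow-up. P(X ≤ 1) then comes from the exact distribution of a sum of unequal Bernoulli variables. With uniform onset, p = 1/3 and 3-day spacing, the six probabilities are 21/63, 19/63, 16/63, 13/63, 10/63 and 7/63, giving 0.587.
- Only week 1 counted: replace p with p·F(7), which is p/3 for uniform onset.

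The stop at ≥2 of the first 3 is contained in ≥2 of 6, so it does not alter these figures.

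| Case | p = 1/3 | p = 0.20 | p = 0.10 |
|---|---|---|---|
| Full 21-day windows | 0.351 | 0.655 | 0.886 |
| Day 22 decision, uniform onset | 0.587 | 0.809 | 0.943 |
| Weekly enrolment, uniform onset | 0.466 | 0.737 | 0.918 |
| Two-weekly enrolment, uniform onset | 0.424 | 0.710 | 0.908 |
| Only week 1 counted, uniform onset | 0.863 | 0.944 | 0.985 |

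If every DLT starts in week 1, all rows equal the first, because each subject has at least 7 days of follow-up. If two-thirds start in week 1 and the rest are uniform over the next 14 days, the figures at p = 1/3 are 0.463 (day 22), 0.407 (weekly), 0.388 (two-weekly) and 0.601 (only week 1 counted).

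**The case against.** The strongest reply is that practice would protect the decision. DLTs are monitored continuously, the team meets weekly about each patient (section 7.6.1), and 1 week is a floor, so waiting 21 days satisfies the timing sentence. A team is unlikely to ignore a known day-15 event that section 3.1.1 calls a DLT. The rows that count only week 1 are therefore the least likely reading and should not carry the argument. The earlier trial of ETBX-011 alone reported no DLT.

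Much of this stands as qualification:

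- Not every related Grade 3 event is a DLT. Section 3.1.1 excepts several transient events and asymptomatic amylase or lipase rises.
- The timing sentence speaks of de-escalation. Applying it to expansion is an inference, though a reasonable one, because the same count decides both.
- The 7-day diary fits a 1-week reactogenicity period.
- A second injection on day 14, which the visit window permits, is a separate and lesser matter. Events on days 14–21 would still count under section 3.1.1.

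The conflict remains. Monitoring does not settle whether a day-15 event counts, or whether the decision must wait for it. The section 8.4.6.2 halting rules need a possibly related death, two Grade 4 events, or more than 33% with Grade 3 or 4 major organ toxicity during expansion. Two Grade 3 DLTs in dose finding trigger none of these. Section 8.4.4 accepts up to 3 DLTs in 10 once expansion is included, which is a later check and does not replace this decision. The ETBX-011 data do not cover three vaccines given together.

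**Conclusion.** The concern holds and should be corrected before the first dose-level decision. The DLT period behind the first-listed primary endpoint has two incompatible values. Under the 1-week text, the earliest permitted decision leaves between 1 of 6 (two-weekly enrolment) and 5 of 6 subjects (3-day spacing) short of 3 weeks. These counts follow from the plan's timing rules and the enrolment pace.

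The effect on the decision depends on onset timing, which the plan does not give. At a true rate of 1/3 and the fastest enrolment, the chance of passing goes from 35% to between 35% (all onsets in week 1) and 59% (uniform onset), with 46% if two-thirds fall in week 1. At a rate of 10% the range is 89–94%. Late events would still be recorded as adverse events. What is undefined is whether they count as DLTs when the dose is chosen.

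**What to change.** - In section 8.4.4, replace both 1-week statements with the 3-week period of section 3.1.1.
- Add that no expansion or MTD decision is made until every subject at the dose level has completed 21 days after the first injection, with the week 3 laboratory results, or has had a DLT.
- Keep immediate de-escalation as soon as a second DLT occurs.
- As a secondary matter, give dose-finding subjects their second vaccination no earlier than day 21, so that the window reflects the first dose alone.

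The cost is a wording amendment and about two more weeks (21 − 7 = 14 days) before each expansion decision. The enrolment ceiling of 32 is unchanged.

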8.4.5 Baseline Descriptive Statistics

Not applicable for this Phase I study.

8.4.6 Planned Interim Analyses and Halting Guidelines

8.4.6.1 Planned interim analysis

Not applicable for this Phase I study.

8.4.6.2 Halting guidelines

The following safety events will trigger a temporary suspension of the study injections:

- Death possibly related to the study agent.
- Two Grade 4 toxicity events that are possibly related to the study agent.
- At any time during the expansion phase > 33% of subjects experience a Grade 3 or 4 major organ toxicity possibly related to study injections.

Assessment of these halting rules is a review of cumulative events for all study participants and should not be confused with reasons for delaying or terminating the treatment schedule of any individual subject.

Treatment may also be suspended for safety concerns other than those described above if, in the judgment of the Investigator, participant safety is threatened

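### Passing the Section 8.4.4 DLT limits in the expansion triggers no automatic pause when enough of the DLTs are Grade 3 non-organ events, and 8.4.4 counts DLTs over 1 week where 3.1.1 sets 3 weeks

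*Combined protocol and SAP*

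**What the plan says.** Section 8.4.4 considers a dose level safe if fewer than 33% "of subjects treated at a dose level experience a DLT", and spells this out as 0 of 3, at most 1 of 6, at most 2 of 9 and at most 3 of 10. For the expansion it adds: "Safety will continue to be monitored among additional subjects treated at the MTD or HTD in the dose expansion component of the study". It refers suspension of injections to 8.4.6.2.

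Sections 3.1.2 and 8.2 attach de-escalation, or a possible amendment, to DLT counts in the first 3 or 6 subjects at a dose. Four more subjects then bring the total at the MTD to 10.

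Section 8.4.6.2 lists three automatic triggers: a possibly related death, two possibly related Grade 4 events, and, at any time in the expansion, "> 33% of subjects experience a Grade 3 or 4 major organ toxicity possibly related to study injections". The Investigator may also suspend treatment for other safety concerns.

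Section 3.1.1 defines a DLT as any possibly related toxicity of Grade 3 or more, with exceptions. These include transient (24 hours or less) "Grade 3 fatigue, skin reactions or rash, headache, nausea, emesis that resolves to Grade" 1 or lower. On timing it says: "For purposes of dose escalation the DLT evaluation period will be for 3 weeks following the first dose of drug". For the individual: "Subjects experiencing a DLT will be removed from protocol therapy".

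Section 8.4.4 gives a different window: "DLTs will be observed for 1 week". The decision on whether to de-escalate is made "at least 1 week after the last subject in the previous dose level has received their first injection".

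**The concern.** The limits for 9 and 10 subjects show that DLT counts were meant to matter in the expansion, yet no action is tied to exceeding them. The only automatic trigger that counts Grade 3 events is restricted to major organ toxicity, a term the plan does not define. Four of ten subjects with possibly related Grade 3 fatigue, skin reaction or headache lasting more than 24 hours would fail the plan's safety criterion and set off nothing automatic. Section 8.2 says the expansion is there to gain more safety data, and 1.2.8 says the combination has not been given to humans before.

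The window conflict affects any DLT count, including the count of 6 that opens the expansion. Under 3.1.1 a Grade 3 event on day 12 is a DLT. Under 8.4.4 it may fall outside observation, and the decision may already have been taken.

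**Working it through.** **1. The plan's limits.** The largest x with x/n below 0.33 is 0, 1, 2 and 3 for n = 3, 6, 9 and 10, which reproduces 8.4.4. The first failing counts in the expansion are 3/7 = 42.9%, 3/8 = 37.5%, 3/9 = 33.3% and 4/10 = 40%. After at most 1 of 6, a third DLT cannot occur before subject 8.

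**2. When the triggers stay silent.** Take all subjects treated at the dose as the denominator. Section 8.4.6.2 is not clear on this, but it describes its review as cumulative over all participants. Suppose the DLTs are all Grade 3. At 4 DLTs in 10, one non-organ event leaves 3/10 = 30% with organ toxicity, so nothing fires. At 3 in 9, one non-organ event leaves 2/9 = 22.2%. Mixed sets can therefore pass silently, as can one Grade 4 non-organ event plus Grade 3 events. If a share q of DLTs is major organ toxicity (an assumption, with independent events), the organ trigger fires at 4 of 10 with probability q^4: 0.5^4 = 6% and 0.75^4 = 32%.

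**3. Chance of crossing the limits.** The documents give no DLT rate, so p is assumed. Outcomes are binomial, and the first 6 are known before the expansion. All figures are conditional on at most 1 DLT in 6.

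- A, all 10 dosed before expansion outcomes are known (4 or more of 10 needed): [P(0/6)·P(4/4) + P(1/6)·P(≥3/4)] / P(≤1/6).
- B, one further subject dosed before each DLT is recognised: enumeration of the four expansion outcomes.
- C, each outcome known before the next subject (3 or more by subject 9): [P(0/6)·P(3/3) + P(1/6)·P(≥2/3)] / P(≤1/6).

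At p = 0.10, P(0/6) = 0.5314, P(1/6) = 0.3543 and P(≤1/6) = 0.8857. Then A = (0.5314×0.0001 + 0.3543×0.0037)/0.8857 = 0.0015, and C = (0.5314×0.001 + 0.3543×0.028)/0.8857 = 0.0118.

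| True DLT rate | P(≤1 of 6) | A | B | C |
|---|---|---|---|---|
| 5% | 96.7% | 0.01% | 0.07% | 0.18% |
| 10% | 88.6% | 0.15% | 0.48% | 1.2% |
| 20% | 65.5% | 1.7% | 3.2% | 6.6% |
| 30% | 42.0% | 6.3% | 9.4% | 16.3% |

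These are upper bounds for the gap, because they treat every DLT as a non-organ Grade 3 event.

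**4. What a pause would spare.** Expected first doses spared, given entry to the expansion, are at most 0.002, 0.016, 0.09 and 0.23 at the four rates (C), and zero under A. If the 3-day minimum spacing of 3.1.2 applies in the expansion, the last three of its four subjects can follow the first within 3 gaps × 3 days = 9 days, inside the 3-week window, so a pause may come too late for any first dose. What remains is later doses, scheduled to week 54, in subjects without a DLT: 8−3 = 5, 9−3 = 6 or 10−4 = 6. If the third DLT among the first 9 is recognised after subject 10 has been dosed without a DLT, the number is 10−3 = 7.

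**5. Plausible rates.** The Grade 3-4 table for ETBX-011 in 11.1.2 covers 34 patients, any attribution, and events in at least 2% of patients; 1/34 = 2.9%, so a single case would appear. It shows no injection site reaction, no headache, 1 fatigue and 2 pain events. One-sided 95% Clopper-Pearson upper limits are 8.4% (0/34), 13% (1/34) and 21% (3/34, fatigue plus pain if in different patients). This is a rough guide: only 6 patients received 5×10^11 VP, and of one vaccine rather than three.

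**6. The window.** Three weeks against 1 week leaves days 8-21, or 14 of 21 days, outside the 8.4.4 count. The timing of DLTs is not documented. For scale, take a true 3-week rate of 20%. If none, half or three quarters of DLTs arise after day 7, and those are not counted, the counted rate is 20%, 10% or 5%. The chance of passing the first 6 is then 65.5%, 88.6% or 96.7% (second column above).

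**The case against.** Reserving automatic halts for death, repeated Grade 4 events and frequent organ toxicity, and leaving prolonged Grade 3 fatigue or rash to judgment, is a defensible choice in a study treating 10 subjects at the MTD. The other safeguards are real. A subject with a DLT stops treatment. Outside the DLT period, 3.3 holds the next vaccination for an injection site reaction above Grade 2 or related organ-function toxicity above Grade 1. The team meets weekly, bases dose-level enrollment on prior toxicity and reports safety concerns to the IRB immediately (7.6.1). Serious events reach the sponsor within one business day (7.3), and the Safety Monitoring Committee may review more often than annually (7.6.3). Unnoticed continuation is unlikely. Section 11.1.2 reports no dose-limiting toxicity with ETBX-011, though under a different definition and with a single vaccine.

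Most of this stands, and it keeps the priority of the pause low. It does not close the gap, because these safeguards act on individuals or leave a trial-level pause to judgment. Section 3.1.1 defines DLTs for dose escalation, but 8.4.4 itself carries the limits on to 9 and 10 subjects.

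On the window, 3.6 expects local reactions over several days, so many relevant events may fall in week 1. That reduces the likely effect but does not reconcile the two sections.

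**Conclusion.** Both points hold. The missing pause is a small gap. At true DLT rates of 10% and 20% the chance of crossing the limits is 0.15-1.2% and 1.7-6.6%, given at most 1 of 6 and on the upper-bound assumption that all DLTs are non-organ Grade 3 events. The benefit lies mainly in booster doses. I rate it optional, or at most a low-priority request. The window conflict is a plain contradiction in the rule that governs dose decisions and should be corrected. Its effect depends on DLT timing, which is unknown.

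A reader might infer three stronger things that the documents do not support:

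- That exceeding the limits means nothing. Under 8.4.4 the dose would no longer count as safe; only a mandatory pause is absent.
- That the organ trigger is simply narrower than a DLT and could be replaced by a DLT count. It covers fewer event types, but it runs throughout the expansion rather than for 3 weeks after the first dose, and it has none of the 3.1.1 exemptions.
- That the gap is likely to bite. True rates of 40-50% would give 15-28% (A) to 29-45% (C), but the ETBX-011 data do not point to such rates for these events.

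**What to change.** 1. In 8.4.4, change both 1-week statements (DLT observation, and the wait before a dose-level decision) to 3 weeks, to match 3.1.1. Cost: two sentences, and up to 3−1 = 2 more weeks before a dose-level decision, which 3.1.1 already implies.

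2. Add a bullet to 8.4.6.2: injections are temporarily suspended pending review if, during the expansion, 3 or more DLTs (3-week window) occur among the first 9 subjects treated at the dose, whenever recognised and even if subject 10 has already been dosed, or 4 or more occur among all 10. Fixing the count to the first 9 matters. If recognised DLTs were counted against everyone treated so far, 3 would pause at 9 but not at 10, and faster enrollment would weaken the safeguard. Use integers, because 3/9 is above 33% but not above one third. The 4-of-10 clause mirrors 8.4.4 and adds no pauses, since 4 of 10 implies at least 3 of the first 9. Cost: an occasional extra temporary pause, with the probabilities in column C (1.2% at a 10% DLT rate, 6.6% at 20%, given at most 1 of 6), including cases that end at 3 of 10.

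3. Keep the major organ trigger beside the new bullet. Defining the term and its denominator would help, but is a matter of detail.

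No new data or staff are needed.
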